# 14.7 Exploratory Analyses

# Overall Survival in the Predefined Biomarker-positive Population

An analysis of Overall Survival (OS) in a predefined biomarker-positive population will be performed. In this analysis, biomarker positive patients will be defined as having nuclear  $\beta$ -catenin positivity on immunohistochemical (IHC) staining of Formalin Fixed Paraffin Embedded (FFPE) archival tissue. OS is defined as the time from randomization to death due to any cause. All analyses for OS in the ITT-March and ITT-May populations will also be performed for OS in the biomarker-positive population, using similar methodology.

# Sparse Pharmacokinetic Analysis

Exploratory analyses will be performed on the bioanalytic data obtained from sparse plasma sampling in order to characterize the population pharmacokinetics of BBI608. Demographic and pathophysiologic factors that affect plasma concentration of BBI608 in this population of patients with pre-treated advanced colorectal carcinoma will be examined. The exposure-response relationship between clinical and safety endpoints and BBI608 exposure will also be examined.

AMEND #2: 2014-FEB-24

#### 15.0 PUBLICATION POLICY

# 15.1 Authorship of Papers, Meeting Abstracts, Etc

- 15.1.1 The results of this study will be published. Prior to trial activation, the chair will decide whether to publish the trial under a group title, or with naming of individual authors. If the latter approach is taken, the following rules will apply:
  - The first author will generally be the NCIC CTG chair of the study.
  - A limited number of the members of the NCIC Clinical Trials Group, the Australasian Gastrointestinal Trials Group and Boston Biomedical Inc. may be credited as authors depending upon their level of involvement in the study.
  - Additional authors, up to a maximum of 15, will be those who have made the most significant
    contribution to the overall success of the study. This contribution will be assessed, in part but
    not entirely, in terms of patients enrolled and will be reviewed at the end of the trial by the
    study chair.
  - In the event of a separate paper dealing with the quality of life outcomes, the first author will generally be the Quality of Life Coordinator on the trial committee.
  - In the event of a separate paper dealing with the health economic outcomes, the first author will generally be the Health Economics Coordinator on the trial committee.
- 15.1.2 In an appropriate footnote, or at the end of the article, the following statement will be made:

"A study coordinated by the NCIC Clinical Trials Group and conducted in collaboration with the Australasian Gastrointestinal Trials Group. Participating investigators included: (a list of the individuals who have contributed patients and their institutions)."

## 15.2 Responsibility for Publication

It will be the responsibility of the NCIC CTG Study Chair to write up the results of the study within a reasonable time of its completion. If after a period of six months following the analysis of study results the draft is not substantially complete, the central office reserves the right to make other arrangements to ensure timely publication.

#### Dissemination of Trial Results

NCIC CTG will inform participating investigators of the primary publication of this trial. The complete journal reference and, if where publicly available, the direct link to the article will be posted on the Clinical Trial Results public site of the NCIC CTG web site (http://www.ctg.queensu.ca).

# 15.3 Submission of Material for Presentation or Publication

Material may not be submitted for presentation or publication without prior review by the NCIC CTG Senior Investigator, Senior Biostatistician, Study Coordinator, NCIC CTG and AGITG Study Chairs and Boston Biomedical, Inc. Individual participating centres may not present outcome results from their own centres separately. Supporting groups and agencies will be acknowledged.

#### 16.0 ETHICAL, REGULATORY AND ADMINISTRATIVE ISSUES

# 16.1 Regulatory Considerations

All institutions must conduct this trial in accordance with International Conference on Harmonization-Good Clinical Practice (ICH-GCP) Guidelines.

The conduct of this trial must comply with local laws and national regulations (e.g. in Canada with Division 5 of the Canadian Regulations Respecting Food and Drugs (Food and Drugs Act), in the United States of America with applicable US FDA Regulations) relevant to the use of new therapeutic agents in the country of conduct.

## 16.2 Inclusivity in Research

Individuals must not be excluded from participation in clinical trials on the basis of attributes such as culture, religion, race, national or ethnic origin, colour, mental or physical disability (except incapacity), sexual orientation, sex/gender, occupation, ethnicity, income, or criminal record, unless there is a valid reason (i.e. safety) for the exclusion.

In accordance with the Declaration of Helsinki and the Tri-Council Policy Statement (TCPS), it is the policy of NCIC CTG that vulnerable persons or groups will not be automatically excluded from a clinical trial (except for incompetent persons) if participation in the trial may benefit the patient or a group to which the person belongs.

However, extra protections may be necessary for vulnerable persons or groups. It is the responsibility of the local investigator and research ethics board (REB) to ensure that appropriate mechanisms are in place to protect vulnerable persons/groups. In accordance with TCPS, researchers and REBs should provide special protections for those who are vulnerable to abuse, exploitation or discrimination. As vulnerable populations may be susceptible to coercion or undue influence, it is especially important that informed consent be obtained appropriately.

Centres are expected to ensure compliance with local REB or institutional policy regarding participation of vulnerable persons/groups. For example, if a vulnerable person/group would be eligible for participation in a NCIC CTG clinical trial under this policy but excluded by local policy, it is expected that they would not be enrolled in the trial. It is the centre's responsibility to ensure compliance with all local SOPs.

It is NCIC CTG's policy that persons who cannot give informed consent (i.e. mentally incompetent persons, or those physically incapacitated such as comatose persons) are not to be recruited into NCIC CTG studies. It is the responsibility of the local investigator to determine the subject's competency, in accordance with applicable local policies and in conjunction with the local REB (if applicable).

Subjects who were competent at the time of enrolment in the clinical trial but become incompetent during their participation do not automatically have to be removed from the study. When re-consent of the patient is required, investigators must follow applicable local policies when determining if it is acceptable for a substitute decision maker to be used. NCIC CTG will accept re-consent from a substitute decision maker. If this patient subsequently regains capacity, the patient should be re-consented as a condition of continuing participation.

## 16.3 Obtaining Informed Consent

Informed consent will be obtained for each participant/potential participant in an NCIC CTG trial, in accordance with ICH-GCP section 4.8. The centre is responsible for ensuring that all local policies are followed.

Additionally, in accordance with GCP 4.8.2, NCIC CTG may require that participants/potential participants be informed of any new information may impact a participant's/potential participant's willingness to participate in the study.

Based upon applicable guidelines and regulations (Declaration of Helsinki, ICH-GCP), a participating investigator (as defined on the participants list) is ultimately responsible, in terms of liability and compliance, for ensuring informed consent has been appropriately obtained. NCIC CTG recognizes that in many centres other personnel (as designated on the participants list) also play an important role in this process. In accordance with GCP 4.8.5, it is acceptable for the Principal Investigator to delegate the responsibility for conducting the consent discussion.

NCIC CTG requires that each participant sign a consent form prior to their enrolment in the study to document his/her willingness to take part. NCIC CTG may also require, as indicated above, that participants/potential participants be informed of new information if it becomes available during the course of the study. In conjunction with GCP 4.8.2, the communication of this information should be documented.

NCIC CTG allows the use of translators in obtaining informed consent. Provision of translators is the responsibility of the local centre. Centres should follow applicable local policies when procuring or using a translator for the purpose of obtaining informed consent to participate in a clinical trial.

In accordance with ICH-GCP 4.8.9, if a subject is unable to read then informed consent may be obtained by having the consent form read and explained to the subject. This process must be thoroughly documented.

### 16.3.1 Obtaining Consent for Pregnancy/Exposure Reporting

Information from and/or about the subject (i.e. the pregnant female, the newborn infant, male partner) should not be collected about or from them unless or until they are a willing participant in the research. The rights and protections offered to participants in research apply and consent must be obtained prior to collecting any information about or from them. If the pregnant female is not a participant in the main trial, consent should be obtained via use of the *exposure*/pregnancy follow-up consent form.

In the case of information collected about a newborn, consent should be provided by the legal guardian. In cases where the legal guardian is the participant in the main trial, consent is obtained via the main consent. If the legal guardian is not the trial participant, consent should be obtained via the exposure/pregnancy follow-up consent.

Participants will not be withdrawn from the main trial as a result of refusing or withdrawing permission to provide information related to the pregnancy/exposure. Similarly, male participants will not be withdrawn from the main study should their partner refuse/withdraw permission.

#### 16.4 Discontinuation of the Trial

If this trial is discontinued for any reason by the NCIC CTG all centres will be notified in writing of the discontinuance and the reason(s) why. If the reason(s) for discontinuance involve any potential risks to the health of patients participating on the trial or other persons, the NCIC CTG will provide this information to centres as well.

If this trial is discontinued at any time by the centre (prior to closure of the trial by the NCIC CTG), it is the responsibility of the principal investigator to notify the NCIC CTG of the discontinuation and the reason(s) why.

Whether the trial is discontinued by the NCIC CTG or locally by the centre, it is the responsibility of the principal investigator to notify the local Research Ethics Board and all clinical trials subjects of the discontinuance and any potential risks to the subjects or other persons.

# 16.5 Retention of Patient Records and Study Files

All essential documents must be maintained as per C.05.012 and in accordance with ICH-GCP.

The Principal Investigator must ensure compliance with the Regulations and the GCP Guideline from every person involved in the conduct of the clinical trial at the site.

Essential documents must be retained for 25 years following the completion of the trial at the centre (25 years post final analysis, last data collected, or closure notification to REB, whichever is later), or until notified by NCIC CTG that documents no longer need to be retained.

In accordance with GCP 4.9.7, upon request by the monitor, auditor, REB or regulatory authority, the investigator/institution must make all required trial-related records available for direct access.

NCIC CTG will inform the investigator/institution as to when the essential documents no longer need to be retained.

### 16.6 Centre Performance Monitoring

This trial is eligible for inclusion in the Centre Performance Index. There are minimum standards for performance. Data is to be submitted by electronic data capture (EDC) according to the schedule in Appendix IV (Documentation for Study).

# 16.7 On-Site Monitoring/Auditing

In addition to the routine review of case report forms and supporting documents sent to the central office, NCIC CTG site monitoring will be conducted at participating centres in the course of the study as part of the overall quality assurance programme. The monitors/auditors will require access to patient medical records to verify the data, as well as pharmacy, essential document binders, standard operating procedures (including electronic information) and ethics documentation.

At any time, your site may be subject to an inspection by a regulatory agency such as the Health Canada Inspectorate or the FDA. Your site may also be subject to an audit by NCIC CTG. Further, the drug company which produces BBI608, Boston Biomedical Inc., has reserved the right to audit participating centres. Audits may only be conducted after consultation with NCIC CTG.

# 16.8 Case Report Forms

A list of forms to be submitted, as well as expectation dates, are to be found in Appendix IV.

This trial will use a web-based Electronic Data Capture (EDC) system for all data collection except patient reported outcomes (Quality of Life, Health Utilities). For details of accessing the EDC system and completing the on-line Case Report Forms please refer to the "Registration/Randomization and Data Management Guidebook" posted on the CO.23 area of the NCIC CTG web-site (www.ctg.queensu.ca).

AMEND #2: 2014-FEB-24

# APPENDIX I - PATIENT EVALUATION FLOW SHEET

Required Investigations	Pre-study (i.e., Pre- treatment)	2 hours after the first dose of BBI608, then as clinically indicated	Every 4 weeks/ 28 days 	Every 8 weeks/ 56 days	At 4 weeks (day 28),8 weeks (day 56), &12 weeks (day 84)	At 4 weeks (day 28),8 weeks (day 56),12 weeks (day 84), 16 weeks (day 112) & 24 weeks (day 168)	At 4 weeks (28 days) post- protocol treatment 	At 4 weeks (28 days) post- protocol treatment, & every 8 weeks (56 days) thereafter (until deterioration to ECOG PS 4 or hospitalization for end of life care)
History & Physical	treatment)	mareacea	20 days	uujs	(day 01)	100)	a causioni	ond of me care)
History & Physical Exam	$\mathbf{X}^2$		X					X
ECOG PS	X		X					X
Weight	X		X					X
Height	X							
Vital signs	X		X					X
Hematology 								
CBC + differential	X		X				X	
Platelet count	X		X				X	
Biochemistry 								
Creatinine  , Total Bilirubin, ALT, Alkaline Phosphatase, LDH, Albumin, Potassium, Magnesium, Phosphate	X		X				X	
Urinalysis	X		X				X	
Economics								
Resource Utilization Assessment			X					X
Cardiology Assessment								
ECG	X	X					X	
Radiology & Imaging 								
CT/MRI scan (as per baseline assessment)	X			$X^6$				
Correlative Studies & Tissue Banking								
Submission of representative block of diagnostic tumour tissue to central bank 								
Blood, plasma, serum, RBC pellet, buffy coat	X				X			
Pharmacokinetics								
Blood collection for sparse PK analysis					$X^8$			

continued on next page ...

Amendment #1: 2013-JUN-12

Required Investigations	Pre-study (i.e., Pre- treatment)	2 hours after the first dose of BBI608, then as clinically indicated	Every 4 weeks/ 28 days 	Every 8 weeks/ 56 days	At 4 weeks (day 28),8 weeks (day 56), &12 weeks (day 84)	At 4 weeks (day 28),8 weeks (day 56),12 weeks (day 84), 16 weeks (day 112) & 24 weeks (day 168)	At 4 weeks (28 days) post- protocol treatment 	At 4 weeks (28 days) post- protocol treatment, & every 8 weeks (56 days) thereafter (until deterioration to ECOG PS 4 or hospitalization for end of life care)
Other Investigations	T							
Pregnancy test, serum or urine (if applicable) 	X		$X^{10}$				$X^{10}$	
Serum CEA	X		X				X	
Adverse Events								
Adverse Event assessment 11. 12	X		X					X
Quality of Life								
EORTC QLQ-C30	X					$X^{13}$		
Health Utilities								
Health Utilities Index (HUI3)	X					$X^{13}$		
Overall Survival								
Assess for survival of patient			X					$X^{14}$

- Patients are to be assessed every 4 weeks (28 days) while on study medication and until the first regularly scheduled 4 week assessment at which the patient has been off study therapy for a minimum of 28 days.
- 2 Medical history must include date of diagnosis including histological documentation of malignancy, documentation of *K-ras* status of tumour, prior anticancer therapy and prior date(s) of disease progression. Note: Documentation of progression, as described in section 10.2, or intolerance, as described in sections 5.1.4, 5.1.5 and/or 5.1.6, must be submitted.
- 3 Bloodwork Timing: Pre-treatment blood draws may be done up to 14 days prior to randomization. Every effort should be made to do interim blood draws within 24 hours of the day specified in the protocol.
- 4 Baseline creatinine or creatinine clearance may be used to demonstrate eligibility as per section 5.1.17
- Tumour measurement and evaluation by RECIST 1.1 criteria. The same method of assessment and the same technique should be used to identify and report each lesion at baseline and at reassessment during treatment. Tumour evaluations will continue until progressive disease is documented (as described in section 10). For patients who remain on protocol therapy after objective disease progression has been documented, no further imaging assessments are mandated, but where these occur as a component of care, tumour measurements and assessment must be reported.
- MPORTANT NOTE: For the first 96 patients, for the first 8-week scan, disease assessment MUST be entered into EDC expeditiously, due to the early stopping rule (DCR at first response assessment to project whether continued treatment with BBI608 would be futile) see section 14.5
- 7 On request by the central tumour bank
- 8 Please refer to the specific Sparse PK sampling laboratory manual for full details about blood collection, storage, and shipment
- 9 In women of childbearing potential only. The minimum sensitivity of the pregnancy test must be 25 IU/L or equivalent units of HCG.
- 10 In women of childbearing potential only a negative pregnancy test must be demonstrated every 4 weeks until 4 weeks after the administration of the final dose of protocol therapy.
- 11 Adverse events will be recorded and graded according to the NCI Common Terminology Criteria for Adverse Events (see Appendix V).
- 12 Adverse event assessment by phone will be performed at 24-48 hours after start of protocol treatment, and at 2 and 6 weeks (i.e. approximately days 14 and 42, respectively) after randomization to assess for tolerability of dosing regimen.
- 13 To be completed in clinic. The patient's responses to the questionnaire questions should be entered into EDC for the applicable reporting period. Note that the completed paper questionnaires can be kept on-site and do not have to be submitted to NCIC CTG.
- 14 In the event that the patient is unable to attend clinic, post-progression follow-up may be by means of telephone contact.

AMEND #3: 2014-OCT-01

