#### 7.3 Registration/Randomization

Patients will be randomized 1:1 between the two treatment arms and the randomization will be provided electronically.

AMEND #2: 2014-FEB-24

Note: The validity of results of the trial depends on the authenticity of, and the follow-up of, all patients entered into the trial. Under no circumstances, therefore, may an allocated patient's data be withdrawn prior to final analysis, unless the participant withdraws from the trial and requests that data collection/submission cease from the point in time of withdrawal.

All eligible patients admitted to the trial will be followed by the coordinating center. It is the responsibility of the physician in charge to satisfy himself or herself that the patient is indeed eligible before requesting randomization.

All randomized patients are to be followed until death or until sites are informed by NCIC CTG that further follow-up is no longer required. The follow-up requirements for ineligible patients who have received no protocol therapy include submission of the Baseline Report plus an annual minimal follow-up form. Data submission for ineligible participants who have received at least one dose of protocol therapy should be followed according to the protocol to allow for treatment and adverse event assessment.

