#### 9.0 EVALUATION DURING AND AFTER PROTOCOL TREATMENT

All patients entered on study must be evaluated according to the schedule outlined in Appendix I with documentation submitted according to the schedule in Appendix IV.

Evaluations will be performed at different intervals throughout the study. If dose delays occur for any reason on the study, other study assessments, including assessment by physician and Quality of Life questionnaires, will not be delayed, but should continue at the time indicated from randomization.

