#### 9.2 Evaluation After Protocol Treatment Discontinuation

Investigations		Timing from Randomization	
Physical Examination	
 
Physical examination
 
Vital signs
 
Weight + ECOG Performance status
 
	Every 4 weeks (every 28 days) after randomization until the first regularly scheduled 4 week	
Economics	Resource Utilization Assessment	assessment at which the patient has been off study therapy for a minimum of 28 days, and every 8	
Adverse Events 	* Adverse Event evaluation must be done at each study visit for the preceding reporting period 	weeks (56 days) thereafter until deterioration to ECOG PS 4 or hospitalization for end of life care.	
Overall Survival	• Assess for survival of patient 	Every 4 weeks (every 28 days) after randomization until the first regularly scheduled 4 week assessment at which the patient has been off study therapy for a minimum of 28 days, and every 8 weeks (56 days) thereafter.	
Other	• Serum or urine pregnancy test 		
Investigations	Serum CEA		
Hematology	CBC + differential, Platelet count	Every 4 weeks (every 28 days) after randomization	
Biochemistry	Creatinine, Total Bilirubin, ALT,     Alkaline Phosphatase, LDH, Albumin,     Potassium, Magnesium, Phosphate	until the first regularly scheduled 4 week assessment at which the patient has been off stud therapy for a minimum of 28 days	
Urinalysis	Dipstick (including protein, specific gravity, glucose and blood)		
Cardiology Assessment	• ECG	At the first regularly scheduled 4 week assessment at which the patient has been off study therapy for a minimum of 28 days	
Radiology & Imaging	• CT/MRI scan as per baseline assessment with tumour measurement and evaluation by RECIST 1.1 criteria 	Every 8 weeks (56 days) after randomization until objective disease progression is documented 	
Correlative Studies & Tissue Banking	• Submission of whole blood sample to central tumour bank 	At 4, 8 and 12 weeks after randomization 	
Quality of Life	• EORTC QLQ-C30 	At 4, 8, 12, 16 and 24 weeks after randomization or	
Health Utilities	• Health Utilities Index (HUI3) 6	until deterioration to ECOG PS 4 or hospitalization for end of life care 	

 Adverse events will be recorded and graded according to the NCI Common Terminology Criteria for Adverse Events (see Appendix V).

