# **Evaluation Post-Unblinding & Permanent Discontinuation**

Following unblinding, patients who have not yet met the primary study endpoint (death), and are currently on protocol therapy (active arm) may receive BBI608 on study based on the clinical judgement of the investigator and local REB approval that this is in the patients' best interest, providing the patient is fully informed and provides consent, if this agent is not a nationally licenced medicinal product and/or are not funded by the normal health care infrastructure. Please refer to sections 9.1.1 and 9.2.1.

	At 4 weeks (28 days) post-	Every 8 weeks (56 days) thereafter (until deterioration to ECOG PS 4 or				
Required Investigations	protocol treatment 	hospitalization for end of life care)				
History & Physical						
History & Physical Exam	X					
ECOG PS	X					
Weight	X					
Vital signs	X					
Hematology						
CBC + differential	X					
Platelet count	X					
Biochemistry						
Creatinine, Total Bilirubin, ALT, Alkaline Phosphatase, LDH, Albumin, Potassium, Magnesium, Phosphate	X					
Urinalysis	X					
Cardiology Assessment						
ECG	X	As clinically indicated				
Radiology & Imaging 						
CT/MRI scan (as per baseline assessment)		No longer required for patients who did not have objective disease progression prior to unblinding. But please report disease assessment data in EDC if done.				
Correlative Studies & Tissue Banking						
Submission of representative block of diagnostic tumour tissue to central bank 		See table above				
Blood, plasma, serum, RBC pellet, buffy coat		See table above				
Adverse Events						
Adverse Event assessment for ongoing and related to BBI608 4.5		X				
New Anti-cancer Therapy						
Reporting of new anti-cancer therapy		X				
Overall Survival						
Assess for survival of patient		X 				
1 D-tit	1.11 . 1 . 1.					

- 1 Patients are to be assessed every 4 weeks (28 days) while on study medication and until the first regularly scheduled 4 week assessment at which the patient has been off study therapy for a minimum of 28 days.

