## APPENDIX IV - DOCUMENTATION FOR STUDY

Follow-up is required for patients from the time of randomization and will apply to all eligible patients.

This trial will use a web-based Electronic Data Capture (EDC) system for all data collection. For details of accessing the EDC system and completing the on-line Case Report Forms please refer to the "NCIC CTG EDC Generic Data Management Guidebook" posted on the CO.23 area of the NCIC CTG web-site (www.ctg.queensu.ca).

The electronic CRFs to be used in this trial, through the EDC system, are as follows:

Electronic Folder	Timing	To be completed electronically	Supporting Documentation Required 
Eligibility Checklist		At the time of randomization	· Consent form 
Baseline Report		Within 2 weeks of randomization	
 
Relevant pathology report(s)
 
KRAS reports
 
Relevant operative report(s)
 
Relevant radiology reports (including CT/MRI abdomen/pelvis, CT/MRI chest, chest x-ray)
 
Tumour Measurement Worksheet
 
ECG report
 

Correlative Studies Report (Tumour and Blood)	Continuous running-log folder See sections 6.0 and 9.0	Information pertaining to  baseline/pretreatment (i.e. tumour specimen information and blood collection for correlative studies) must be completed within 2 weeks of randomization.  Tissue to be submitted immediately upon request.  Information pertaining to post randomization blood collection samples (i.e. whole blood, plasma, serum, RBC pellet, buffy coat) for correlative studies and banking should be completed within 2 weeks after collection of final blood specimen.  Information pertaining to blood	
 
Consent form^2
 
Diagnostic pathology report (for tumour tissue only)
 

		collection for Pharmacokinetics must be completed in EDC in real-time, as soon as the sample is collected.	
Concomitant Medication Report	Continuous running-log folder		
Treatment Report	Every 4 weeks (28 days)	Within 2 weeks of the end of each 4 week reporting period	If available/applicable: CT/MRI abdomen/pelvis report  CT/MRI chest  Other radiology reports  Tumour Measurement Worksheet  ECG report
End of Treatment Report 	As soon as permanent off treatment status is confirmed.	Within 2 weeks of end of treatment	ECG report

continued on next page ...

AMEND #2: 2014-FEB-24

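### Both Appendix I flow sheets end off-treatment survival assessment at ECOG PS 4 or end-of-life admission, contradicting sections 7.3, 9.2 and 9.2.1 on follow-up for the primary endpoint

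*Protocol*

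**What the plan says.** **Flow sheets.** In the main Appendix I table the row "Assess for survival of patient" has two marks. One is in the 4-weekly column, which by footnote 1 runs to the first scheduled 4-week assessment at which the patient has been off therapy at least 28 days. The other, the only mark for the period after that, is in the last column, headed "every 8 weeks (56 days) thereafter (until deterioration to ECOG PS 4 or hospitalization for end of life care". Footnote 14 on that mark reads "In the event that the patient is unable to attend clinic, post-progression follow-up may be by means of telephone contact". In the post-unblinding table the survival mark is again in the last column, headed "Every 8 weeks (56 days) thereafter (until deterioration to ECOG PS 4 or" and continuing with end-of-life hospitalization.

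**Status of the flow sheets.** Section 9.0: "All patients entered on study must be evaluated according to the schedule outlined in Appendix I".

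**Body of the protocol.** Section 7.3: "All randomized patients are to be followed until death or until sites are informed by NCIC CTG that further follow-up is no longer required". Section 9.2 applies the limit "deterioration to ECOG PS 4 or hospitalization for end of life care" to physical examination, resource use and adverse events. It gives overall survival a separate timing cell that continues every 8 weeks with no end condition. Section 9.2.1, for the period after unblinding, also has survival every 8 weeks, and the PS 4 limit appears nowhere in its table.

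**Who is followed.** Appendix IV: "Follow-up is required for patients from the time of randomization and will apply to all" *eligible* patients, with *eligible* underlined. Sections 10.1.2 and 14.2 include all randomized patients in the survival analysis, by intention to treat.

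**The concern.** The instructions disagree on when contact for the primary endpoint may stop. The flow sheet is what site staff are likely to work from, and section 9.0 makes it binding. Followed literally, it ends scheduled survival contact when a patient becomes completely disabled or is admitted for terminal care, which is when death is likely to be near.

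Sections 10.1.2 and 14.2 censor patients lost to follow-up at the date last known alive. A patient whose site stopped contact at PS 4 and never learned of the death would be censored there. Such censoring is informative, because the patient's risk of death is far above that of patients still under observation. Each such case also removes an event from a final analysis that is triggered by a death count.

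The word *eligible* in Appendix IV is a second, smaller mismatch. Section 5.1.21 and section 13.3 allow a patient to be declared ineligible after randomization, if tissue is not submitted on request. That patient remains in the intent-to-treat survival analysis but, on the wording of Appendix IV, falls outside the follow-up requirement.

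**Working it through.** **1. The plan's own figures (section 14.3 and the amended section 14.5).**

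- Inputs: HR 0.77, power 90%, two-sided alpha 5%, 1:1 allocation, 615 deaths stated. Schoenfeld: d = 4(z₀.₉₇₅ + z₀.₉₀)² / (ln HR)² = 4(1.960 + 1.282)² / (0.2614)² ≈ 615.3, or 616 rounded up. The stated 615 is reproduced.
- Amended final analysis: 195 events. Power = Φ(√d/2 × |ln HR| − 1.960).
  - HR 0.70: Φ(6.982 × 0.3567 − 1.960) = 70.2%, against 70% stated.
  - HR 0.77: Φ(6.982 × 0.2614 − 1.960) = 44.6%, against 43% stated, a difference of under 2 points.

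These figures stand. The contradiction concerns how deaths are collected, not how many are needed.

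**2. How complete death capture must be.**

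- Initial design: take exponential survival (an assumption) with medians of 4.6 and 6.0 months, uniform accrual over A = 26 months and F = 12 further months. Then P(death) = 1 − [e^(−λF) − e^(−λ(A+F))] / (λA), with λ = ln 2 / median. This gives 0.959 and 0.921, so 325 × (0.959 + 0.921) ≈ 611 deaths expected among 650. The target of 615 is therefore about every death that would occur by the planned end.
- Amended design: 0.90 × 217 = 195.3, hence 195. The margin is 217 − 195 = 22 patients, and 22/217 = 10.1%. It covers every reason for having no recorded death: still alive, withdrawn, lost, or dead without the site knowing. With 23 such patients the count is 217 − 23 = 194 and the trigger is not met.

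Both event counts presuppose follow-up to death, as section 7.3 requires. Neither fits a literal stop at PS 4.

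**3. The passages side by side: when does off-treatment survival contact end?**

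- Section 7.3: at death, or when sites are told to stop.
- Section 9.2: 8-weekly, no end condition.
- Section 9.2.1: 8-weekly, no end condition.
- Appendix I, main table: at PS 4 or end-of-life admission.
- Appendix I, post-unblinding table: at PS 4 or end-of-life admission.

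Footnote 14 does not resolve this: it changes the mode of contact, not its duration. The separate survival cell in section 9.2 shows the intent, since the limit was kept for examination, resource use and adverse events and left off for survival. The shared column in the main flow sheet loses that distinction. The post-unblinding sheet is the more consequential of the two. It covers patients off treatment after 23 May 2014, when all were directed to stop protocol therapy apart from case-by-case continuation, and it is from such patients that most of the outstanding deaths for the final analysis would have to come.

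**The case against.** The strongest reply is that the protocol, read as a whole, leaves little doubt. Section 12.4 deals specifically with follow-up off treatment and names section 9.2 as the plan. The post-unblinding flow sheet itself refers readers to sections 9.1.1 and 9.2.1. Appendix IV requires a Death Report upon death, whatever the visit schedule, and its 8-weekly Follow-up Report covers all patients who have permanently stopped study drug, with no PS 4 limit. Section 7.3 keeps ineligible patients who took at least one dose on full follow-up, so the *eligible* wording has limited practical reach.

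Most of this stands, and it confines the point to a contradiction between passages. It does not remove it. A Death Report can be filed only if the site knows of the death, and scheduled contact is how a site learns of a death outside its own hospital. The cross-references also point both ways: section 12.4 sends the reader to section 9.2, while section 9.0 sends the reader to Appendix I.

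A reader might infer something stronger: that deaths will be censored just before they occur. The protocol does not support that. No passage makes PS 4 or hospitalization a censoring event; only patients alive at the final analysis or lost to follow-up are censored. Nor can lost power or an inflated median be calculated, because the protocol gives no share of deaths that would go unrecorded.

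**Conclusion.** The contradiction is real, occurs in both flow sheets, and affects the primary endpoint. Its consequence is conditional. If a site follows the flow sheet and not sections 7.3, 9.2 or 9.2.1, deaths may be missed or learned of late, and the patients concerned would be censored near death. The frequency is unknown. The direction of any effect on the comparison between arms is also unknown, since it depends on whether the loss differs by arm.

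The one firm measure is the margin: 22 of 217 patients (10.1%) may lack a recorded death, for any reason, before the 195-event trigger is out of reach. The stated 615 deaths and the 70% power at HR 0.70 are reproduced, and no sample size or power figure needs to change. The *eligible* wording in Appendix IV is a lesser inconsistency with section 7.3 and with the intent-to-treat analysis. The annual minimal follow-up that section 7.3 sets for untreated ineligible patients is a stated choice and is not part of this point.

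**What to change.** - In both Appendix I tables, move the survival row to its own column, or attach a footnote, so that it agrees with sections 7.3 and 9.2: every 8 weeks until death or until sites are told to stop, by telephone where the patient cannot attend, with no PS 4 or end-of-life limit. Where section 9.2 places the limit on other assessments, it can stay for them.
- In the follow-up statement at the start of Appendix IV, replace *eligible* with *randomized*, leaving the section 7.3 arrangement for untreated ineligible patients as it is.

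The cost is a wording change in two tables and one sentence. Sites already working to section 7.3 take on nothing new; others would make a few more telephone or record checks. No analysis, event count or power statement changes.
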